9.4.2 Non-Serious Adverse Events

The recording of non-serious AEs will begin after the patient signs the informed consent form and will stop at the end of the patient's follow-up period. The Investigator will monitor each patient closely and record all observed or volunteered AEs on the Adverse Event Case Report Form.

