- **Persists (as non-serious AE):** Patient has not fully recovered but the event no longer meets serious criteria and should be captured as an AE on the non-serious eCRF (the SAE resolution date should be entered as the date of onset of that AE)

- **Recovered:** Patient recovered completely from the SAE (the date of recovery should be entered as the SAE resolution date)
- **Fatal:** Patient died (the date of death should be entered as the SAE resolution date)

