3.7.1 Imputation of Missing/Partial Dates

3.7.1.1 Adverse Events

For AEs, the following imputation rules will be applied to impute start dates under conservative principles:

- If year, month and day are all missing then assign the date of first dose of Study Drug
- If month and day are missing, and year is:
 - the same as the year of the first dose of Study Drug then assign the month-day of first Study Drug
 - earlier than the year of the first dose of Study Drug then assign December 31
 - after the year of the first dose of Study Drug then assign January 1
- If only day is missing, and month-year is:
 - the same as the month-year of the first dose of Study Drug then assign the day of first Study Drug
 - earlier than the month-year of the first dose of Study Drug then assign the last day of the month
 - after the month-year of the first dose of Study Drug then assign the first day of the month

Imputation will be performed for the end date only if the day or month is missing (i.e., year is present) for a resolved AE as follows:

- If month and day are missing, and year is
 - the same as the year of the last dose of Study Drug then assign the month-day of the last dose of Study Drug
 - otherwise, assign December 31
- If only day is missing, then assign the last day of the month

If the imputed start date is later than the imputed end date, then set the imputed start date to the imputed end date.

Analysis period (on-treatment and on-study) will be assigned by comparing the imputed AE start date with the period start/end date.

3.7.1.2 *Prior/Concomitant Medications*

For prior/concomitant medications, the following imputation rules will be applied to impute start dates under conservative principles:

- If year, month and day are all missing, then assign the date of first dose of Study Drug
- If month and day are missing and year is:
 - earlier than the year of the first dose of Study Drug then assign December 31
 - otherwise, assign January 1
- If only day is missing, and month-year is:
 - earlier than the month-year of the first dose of Study Drug then assign the last day of the month
 - otherwise, assign the first day of the month

Imputation will be performed for the end date only if the day or month is missing (i.e., year is present) for a stopped prior/concomitant medication as follows:

- If month and day are missing, then assign December 31
- If only day is missing, then assign the last day of the month

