If the imputed start date is later than the imputed end date, then set the imputed start date to the imputed end date.

Analysis period will be assigned by comparing the imputed medication start/end date with the period start/end date.

3.7.2 *Adverse Events*

All AEs will be coded by the Medical Dictionary for Regulatory Activities (MedDRA) version 20.1. Missing or partial dates will be imputed as outlined in Section 3.7.1.

Treatment-emergent adverse events (TEAEs) are defined as adverse events that occurred after the first dose of Study Drug. If the imputed onset date/time is the same as or after the date/time of the first dose of Study Drug, then the event is treatment emergent. An AE with a completely missing start date will be assumed to be treatment emergent.

In the situation where change in severity (but no change in seriousness) occurs for an AE, study sites are instructed to enter an end date for the original AE and start a new record for the AE with a new severity reported. In the new record, the changed severity is to be recorded and the start date will be set to be the end date of the previous record.

When counting the total number of treatment-emergent events for table display, events reporting an increase in severity will be counted as separate events.

AE summary tables by treatment group and overall will be presented in 2 periods separately: on-treatment and on-study. The frequency of patients with any incidence of AEs and the number of events will be summarized by SOC and PT for:

- TEAEs
- TEAEs related to Study Drug. Related is defined as “Related”, “Possible”, or missing relationship to Study Drug
- TEAEs by severity. At each level of patient summarization, a patient with multiple events is counted only once according to the worst reported severity. Adverse events with missing severity will be categorized as “Missing” for this summary.
- TEAEs related to Study Drug by severity
- Most common TEAEs. Most Common TEAE is defined as treatment-emergent adverse events with an incidence of 10% or more within any treatment groups at PT level.
- Treatment Emergent SAEs
- Treatment Emergent SAEs related to Study Drug
- TEAEs leading to permanent treatment discontinuation
- TEAEs leading to death.

Summary tables will be sorted by decreasing frequency of SOC and then by decreasing frequency of PT within SOC in pooled ISIS 678354 group. If the frequency is the same for multiple PTs, sort alphabetically.

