An overview of AEs will be provided for all TEAEs. Treatment-emergent AEs, treatment-emergent SAEs, TEAEs related to Study Drug, treatment-emergent SAEs related to Study Drug, TEAEs that lead to Study Drug discontinuation, TEAEs that lead to Study Drug interruption, TEAEs that lead to dose reduction, and TEAEs leading to death will be listed. Note that imputed dates will be used for defining TEAEs and classification of TEAEs into analysis periods.

Listings of all AEs, TEAEs related to Study and Treatment Emergent SAEs related to Study will be presented. Originally reported dates will be used in listings.

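### Read literally, the SAP's onset-date rule flags an adverse event that began before the first dose and then improves as treatment-emergent

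*Combined protocol and SAP*

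**What the plan says.** Protocol 9.4.2 sets when collection starts: "The recording of non-serious AEs will begin after the patient signs the informed consent form". Screening lasts up to 4 weeks (Protocol 3.4.1), so records can be open on Day 1. Conditions already present at consent go to medical history unless they worsen (Protocol 9.4).

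SAP 3.7.2 deals with a change in severity that leaves seriousness unchanged. The site ends the existing record and must "start a new record for the AE with a new severity reported"; for that record, "the start date will be set to be the end date of the previous record". The instruction covers change in either direction.

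Protocol 9.4.3.5 splits records in a similar way when seriousness changes. The outcome *Became Serious* opens an SAE record dated from the change. The outcome *Persists* covers the reverse: "Patient has not fully recovered but the event no longer meets serious criteria and should be captured as an AE on the non-serious eCRF".

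SAP 3.7.2 then applies the TEAE test: an event qualifies "If the imputed onset date/time is the same as or after the date/time of the first dose of Study Drug". The same section adds: "Note that imputed dates will be used for defining TEAEs and classification of TEAEs into analysis periods". Under SAP 3.7.1.1 the analysis period "will be assigned by comparing the imputed AE start date with the period start/end date". One further sentence in SAP 3.7.2 concerns the counting of events for tables: "events reporting an increase in severity will be counted as separate events".

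**The concern.** A treatment-emergent event should be one that starts, or gets worse, after the first dose. The SAP tests only when a record starts, while its own data-entry rule creates new start dates for events that are already under way. An event that began in screening and is resolving can therefore acquire a post-dose date and pass the test.

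Safety is part of the primary objective, and each regimen has only about 20 treated patients, so single patients are visible in the incidence columns. The patient column and the event column of one table can also disagree, because the SAP considers the direction of a severity change for event totals but not for the flag.

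**Working it through.** The plan gives no figure to reproduce. The check applies the rules to constructed histories and then works out the weight of one patient.

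**Inputs.** First dose = Day 1. A record is flagged if its start is on or after Day 1 (SAP 3.7.2). A patient counts if any record is flagged. Event totals are shown on two readings: every flagged record counts, or a continuation record counts only if severity rises. The last column applies the rule proposed under the fix.

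| History | Patient counted as written | Events: all flagged records | Events: increases only | Patient counted after fix |
|---|---|---|---|---|
| Moderate from Day −10, mild from Day 5 | yes | 1 | 0 | no |
| Mild from Day −10, moderate from Day 5 | yes | 1 | 1 | yes |
| Moderate from Day −10, unchanged | no | 0 | 0 | no |
| Mild from Day 3, moderate from Day 5 | yes | 2 | 2 | yes |
| Moderate from Day 3, mild from Day 5 | yes | 2 | 1 | yes |
| Severe then mild in screening, moderate after first dose | yes | 1 | 1 | yes |

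The first row is the problem. The original record is not flagged, the Day 5 record is, and the patient enters the table with mild as the worst treatment-emergent severity. On the increases-only reading the row shows 1 patient and 0 events. The third row shows the anomaly from the other side: the same event, had it not improved, would not be counted.

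**Weight of one patient.** Each cohort has about 25 patients, randomized 4:1.
- Active, per regimen: 25 × 4/5 = 20.
- Pooled placebo: 25 × 1/5 × 4 = 20.
- One patient: 1/20 = 5 percentage points. This is a maximum, since a patient who already has another TEAE in the same row is counted once anyway.
- The 10% cut-off for most common TEAEs is 0.10 × 20 = 2 patients. It applies at preferred-term level, so two spurious cases reach it only if they share a term.

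**Effect on a between-group difference.** Let f be the chance that a patient has such a record, equal in all arms and independent of genuine TEAEs. Observed any-TEAE risk is p + f(1 − p), so the difference becomes (1 − f)(p₁ − p₀). The documents give no f. For illustration only, assume 10–20% of patients have an event open at first dose and one third to one half of these record a lower grade before it resolves:
- f = 0.10 × 1/3 = 3.3% to 0.20 × 1/2 = 10%.
- The true difference is multiplied by 0.967 to 0.90.

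That is a slight attenuation, with no direction in favour of any arm.

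**The case against.** The strongest reply is that the text is ambiguous. SAP 3.7.2 tests the onset of the event, describes the new entry as a record for the same AE, and opens by defining TEAEs as events occurring after the first dose. On that view a continuation keeps its original onset. This has some force, because the SAP never says outright which date applies. The surrounding text points the other way. SAP 3.7.1.1 imputes start dates, SAP 3.7.2 then refers to the imputed onset, and Protocol 9.4.3.5 explicitly treats the date of a seriousness change as the onset of the new record. A programmer working from these documents would use the new record's date.

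A second reply is that the sentence on severity increases already excludes improvements. It may do so for event totals, but it does not govern the flag, the patient counts or the listings.

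A third is that over-inclusion is the cautious error in safety reporting. That is fair as to direction. However, the conservative principle stated in SAP 3.7.1.1 concerns incomplete dates, not continuation records.

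Several stronger readings are tempting, but the documents do not support them:
- *Pre-existing conditions in general become TEAEs.* Conditions present before consent are medical history unless they worsen (Protocol 9.4). Only events that begin or worsen between consent and first dose, and are still open at first dose, are exposed.
- *Every TEAE table is distorted.* An improved record on the three-level scale is at most moderate, so the severe row cannot gain. An event judged possibly related needs a plausible temporal link to dosing (Protocol 9.4.3.1), so related tables are barely exposed, apart from a missing relationship, which the SAP counts as related. SAE and death tables are also barely exposed, and discontinuation tables are unlikely to move.
- *The comparison with placebo is biased.* Nothing suggests different rates by arm, and Protocol 10.6 confines hypothesis testing to efficacy endpoints.
- *A specific share of patients is misclassified.* No rate can be derived from the documents.

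**Conclusion.** The point holds as a flaw in a stated rule, with limited reach. Taken literally, SAP 3.7.2 classes an improving event that began before dosing as treatment-emergent. The parts affected are the flag itself, patient incidence, the mild and moderate severity rows, and the listings; patient and event counts can also contradict each other. The conclusion rests on reading onset as the start date of each record, which is the more natural reading but not a stated one.

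The frequency is unknown. Each case is worth at most 5 percentage points in a group of about 20. The seriousness route through *Persists* is marginal, since it needs an SAE in screening in a patient who is still randomized and dosed. The flaw does not threaten the trial's conclusions, but it should be corrected because the remedy is simple.

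**What to change.** In SAP 3.7.2:
- Link continuation records, identified by the outcomes *Change in Severity*, *Became Serious* and *Persists*, to the original AE, and judge treatment emergence on the original onset.
- State that a continuation of a pre-dose AE is treatment-emergent only if its severity or seriousness after the first dose exceeds the level in effect at first dose.
- Apply the same flag to patient counts and event counts.

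The comparator matters. Using the worst level at any time before dosing would drop the last history in the table above: the event eased in screening and then worsened on Study Drug, but never regained its earlier peak. The level in effect at first dose keeps it.

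The cost is a short SAP rule and a small record-linking step in programming. No new data are needed, because the outcome codes are already collected. The downside is slightly fewer flagged events. Genuine worsening stays flagged, and events that start after dosing keep their treatment-emergent status.

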3.7.2.1 Treatment Emergent Adverse Events at Injection Site

Treatment Emergent AEs at injection site will follow two definitions:

Definition 1: Local cutaneous reactions at injection site (LCRIS) are defined as injection site erythema, injection site swelling, injection site pruritus, injection site pain, or injection site tenderness that started on the day of injection and persisted for at least two days (i.e. event onset date on the day of injection and resolution date not on the day of injection or the day after injection) will be included. Events on the day of the injection with a missing resolution date will also be included.

Definition 2: Injection Site Reactions (ISR) are defined as any AE with PT or verbatim term containing ‘Injection Site’ that persisted for at least two days (i.e. event onset date on the day of

injection and resolution date not on the day of injection or the day after injection) will be included. Events with a missing resolution date will also be included.

Treatment Emergent LCRIS will be summarized by SOC and PT and by severity in on-treatment period only. Treatment Emergent ISRs will be summarized by SOC and PT and by severity in on-treatment and on-study periods.

Additionally, the following will be summarized using Definition 2 (i.e., ISRs):

- Percentage of injections leading to ISR for overall and preferred term will be summarized using descriptive statistics for on-study period only. Percentage of injections leading to ISR will be calculated as follows for each patient: $(A/B) * 100$, where A = number of injections leading to ISR, and B = total number of injections.
- ISRs by injection location for on-study period only
- Incidence of ISR and time to first ISR for on-study period only
- ISRs by treatment time interval (≤ 13 weeks, $>13-26$ weeks, $>26-39$ weeks, and $>39-52$ weeks) for on-treatment period only

An additional table summarizing ISRs (definition 2) on-treatment by SOC and PT and by severity within cohort will be presented.

3.7.2.2 *Treatment Emergent Flu-Like Reactions*

Treatment Emergent Flu-Like Reactions (FLRs) will follow two definitions:

- Definition 1: TEAEs with either (i) influenza like illness or (ii) at least one of following PTs: pyrexia, feeling hot, or body temperature increased, plus at least two of the following PTs: chills, myalgia, and arthralgia, starting on the day of injection or the next day.
- Definition 2: TEAEs with following PTs or verbatim: influenza like illness, chills, myalgia, arthralgia, pyrexia, feeling hot, or body temperature increased, starting on the day of injection or the next day.

Note that imputed dates will be used for defining.

Treatment Emergent FLRs defined in definition 1 will be summarized by category (i) or (ii). Treatment Emergent FLRs defined in definition 2 will be summarized by SOC and PT. Both definitions will be presented in on-treatment period.

Percentage of injections leading to FLRs (definition 2) for overall and by preferred term will also be summarized using descriptive statistics. Percentage of injections leading to FLRs will be calculated for each patient as $(A/B) * 100$, where A is the number of injections associated with FLRs, and B is the total number of injections.

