3. EXPERIMENTAL PLAN

3.1 Study Design

This is a multicenter, randomized, double-blind, placebo-controlled, dose-ranging study. After an up to 4-week screening period, including an up to 2-week qualification period following an at least a 2-week diet stabilization period, where appropriate, approximately 100 eligible patients will be randomized in a 4:1 ratio to receive ISIS 678354 or placebo. Patients on a stable diet known to the investigator and followed at the site may go from Screening to qualification period without a 2-week diet stabilization phase. Study Drug (ISIS 678354 or placebo) will be administered by subcutaneous (SC) injection every week, every 2 weeks, or every 4 weeks, depending on cohort assignment, for up to 52 weekly doses, up to 26 every 2-week doses, or up to 13 every 4-week doses. Minimum treatment duration is 6 months. Maximum treatment duration is 12 months

The treatment portion of the study will be complete when the last patient reaches 6 months of exposure. All patients still on treatment will then enter a 13-week post-treatment follow-up period. Refer to [Section 3.4.2](#) for additional detail regarding End of Treatment period and scheduling of End of Treatment Visits.

The primary efficacy and safety analysis time point is at Week 25 for patients who received every 4-week dosing (Cohorts A and B) and at Week 27 for patients who received every 2-week or weekly dosing (Cohorts C and D, respectively). For patients continuing treatment beyond the primary analysis time point additional supportive efficacy and safety analyses will be repeated at the completion of Study Drug treatment.

Patients ≥ 18 and ≤ 80 years old with elevated plasma TG levels (≥ 200 mg/dL (≥ 2.3 mmol/L) and ≤ 500 mg/dL (≥ 5.7 mmol/L)) and a clinical diagnosis of CVD or at high risk for CVD are eligible for enrollment upon meeting the study specific eligibility criteria. Patients will be on standard-of-care preventative therapy for known CVD risk factors as per current guidelines.

Clinical diagnosis of CVD is defined as documented coronary artery disease (CAD), stroke, or peripheral artery disease (PAD). A diagnosis of CAD has to be documented by any of the following:

- Angiographic evidence of $\geq 50\%$ stenosis of 1 or more major epicardial coronary arteries
- History of myocardial infarction documented by positive enzymes, and either symptoms of myocardial ischemia, or ECG changes ([Thygesen et al. 2012](#))
- History of coronary revascularization

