1.1 Study Overview

The study ISIS 678354-CS2 is a Phase 2 multicenter, randomized, double-blind, placebo-controlled, dose-ranging study being conducted at approximately 32 sites in the United States and Canada.

Patients ≥ 18 and ≤ 80 years old with elevated plasma triglyceride levels (≥ 200 mg/dL (≥ 2.3 mmol/L) and ≤ 500 mg/dL (≥ 5.7 mmol/L)) and a clinical diagnosis of established CVD, or at high risk for CVD (as defined in the study protocol), will be eligible for enrollment upon meeting the study specific eligibility criteria. Patients will be on standard-of-care preventative therapy for known CVD risk factors as per current guidelines. The study is comprised of the following periods:

- **Screening:** An up to 4 week Screening Period, including an up to 2-week qualification period following an at least 2-week diet stabilization period, where appropriate. Patients on a stable diet known to the investigator and clinically followed at the site may go from Screening to the qualification visit without a 2-week diet stabilization phase.
- **Treatment Period:** Following qualification, up to approximately 100 eligible patients will be randomized in a 1:1:1:1 ratio to one of the 4 dosing cohorts as shown in [Table 1](#), with each cohort having a 4:1 ratio to receive ISIS 678354 or matching volume of placebo, respectively, by SC injection.

Table 1: Study Drug Dosing Information

Cohort	Treatment	Volume to Administer/Dose	# Doses	Total ISIS 678354
A	10 mg ISIS 678354 or placebo (Every 4 weeks)	0.10 mL	≤ 13	≤ 130 mg
B	50 mg ISIS 678354 or placebo (Every 4 weeks)	0.50 mL	≤ 13	≤ 650 mg
C	15 mg ISIS 678354 or placebo (Every 2 weeks)	0.15 mL	≤ 26	≤ 390 mg
D	10 mg ISIS 678354 or placebo (Every week)	0.10 mL	≤ 52	≤ 520 mg

The minimum treatment duration for all patients is 6 months and the maximum is 12 months. The treatment portion of the study will be complete when the last patient reaches 6 months of exposure, at which time patients still receiving Study Drug (ISIS 678354 or placebo) will transition to the Post-Treatment Follow-up Period.

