2.2 Randomization and Treatment Allocation

Patients will be randomized after all screening and qualification assessments have been completed and after the Investigator has verified, they are eligible per criteria in the protocol sections 5.1 and 5.2. No patient may begin treatment prior to randomization and assignment of a unique patient identification number.

Using an Interactive Web-Response System (IWRS), eligible patients will be randomized in a 1:1:1:1 ratio to 1 of the 4 parallel-dose cohorts (Cohorts A, B, C or D). Within each dose cohort, patients will be randomized in a 4:1 ratio to receive ISIS 678354 or matching volume of placebo, respectively.

A permuted block schedule will be used. The randomization schedule will be generated and held by an independent vendor. Patients who withdraw from the study will not be replaced. The study is planned to randomize approximately 100 patients.

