3 ANALYSIS PLANS

3.1 Statistical Design Summary

This is a multi-center, randomized, double blind, placebo-controlled study.

The study hypotheses will be formally evaluated at the planned EoT analysis on data obtained through the data cut-off date, defined as the date of the last EoT visit. The database will be queried, and data cleaning performed on all data, with database interim lock of all data, at which point the treatment code is unblinded and the EoT analysis is performed.

The primary analysis model will be an Analysis of Covariance (ANCOVA) model for percent change from baseline to the PAT in fasting triglycerides. Missing data will be imputed by a multiple imputation method as the primary analysis and will be supported by various sensitivity analyses.

The treatment groups proposed in this analysis are defined as follows:

- ISIS 678354 10 mg every 4 weeks (Q4W)
- ISIS 678354 50 mg every 4 weeks (Q4W)
- ISIS 678354 15 mg every 2 weeks (Q2W)
- ISIS 678354 10 mg every week (QW)
- Pooled Placebo, defined as the combined group of placebo patients from the 4 randomized cohorts

A final analysis will be performed after all data from the 13-week post treatment follow-up period are collected and locked.

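### Per-patient tables of flu-like and local skin reactions compare each regimen with placebo pooled over different injection frequencies, so frequency alone can shift the arm-by-arm comparison; only some of these measures have a per-injection display

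*Combined protocol and SAP*

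**What the plan says.** **Comparator.** SAP 3.1 lists four active groups and one placebo group: "Pooled Placebo, defined as the combined group of placebo patients from the 4 randomized cohorts". SAP 3.7.2 presents adverse event tables by treatment group, as patients with an event and number of events.

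**Allocation.** SAP 2.2 states that "eligible patients will be randomized in a 1:1:1:1 ratio to 1 of the 4 parallel-dose cohorts", and then: "Within each dose cohort, patients will be randomized in a 4:1 ratio to receive ISIS 678354 or matching volume of placebo, respectively". Placebo patients follow their own cohort's schedule, which Protocol 3.1 gives as "for up to 52 weekly doses, up to 26 every 2-week doses, or up to 13 every 4-week doses". SAP 1.1 adds: "The minimum treatment duration for all patients is 6 months and the maximum is 12 months".

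**Flu-like reactions (SAP 3.7.2.2).** Definition 2 takes any one of a list of terms, including chills, myalgia, arthralgia and pyrexia, "or body temperature increased, starting on the day of injection or the next day". Definition 1 uses the same two-day window. It requires either influenza-like illness or a fever-type term with at least two of chills, myalgia and arthralgia. Definition 1 is summarised by category and Definition 2 by SOC and PT. For Definition 2 the SAP also plans the percentage of each patient's injections that lead to an FLR, overall and by PT.

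**Local skin reactions (SAP 3.7.2.1).** LCRIS covers five injection-site terms that start on the injection day and persist. The only display planned for it as a composite is this: "Treatment Emergent LCRIS will be summarized by SOC and PT and by severity in on-treatment period only". ISR Definition 2 covers any event with an injection-site term under the same persistence rule. It gets a percentage-of-injections summary, overall and by PT, and also: "An additional table summarizing ISRs (definition 2) on-treatment by SOC and PT and by severity within cohort will be presented". SAP 3.7.2.3 plans a within-cohort table for bleeding as well. No within-cohort table is planned for FLR.

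**The concern.** An event enters the FLR or LCRIS tables only if its onset is tied to an injection. A weekly patient offers four times as many qualifying occasions as a 4-weekly patient over the same calendar time. Pooled placebo sits at the average of the four schedules, so it matches the 2-weekly arm but not the others. In a per-patient table, the weekly arm can then show an excess over placebo that the drug did not cause. A 4-weekly arm can show a deficit. The second error is the more serious, because it can hide a real effect.

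Arm-by-arm reading is the purpose of a dose-ranging study. The synopsis says safety and tolerability on active drug will be compared with placebo. Protocol 2.4 makes good tolerability a condition for the possible advantage of less frequent dosing over weekly dosing.

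**Working it through.** **1. The plan's own dose figures.** Doses run from Week 1 to Week 49 (A, B), Week 51 (C) and Week 52 (D).
- A and B: (49 − 1)/4 + 1 = 13 doses; 13 × 10 = 130 mg and 13 × 50 = 650 mg.
- C: (51 − 1)/2 + 1 = 26 doses; 26 × 15 = 390 mg.
- D: 52 doses; 52 × 10 = 520 mg.

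All four rows match Protocol Table 2 and SAP Table 1.

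**2. Calendar time.** SAP 3.7 defines on-treatment as first dose to last dose plus one interval. At the maximum this is 13 × 28 = 26 × 14 = 52 × 7 = 364 days in every cohort, so follow-up time does not offset the difference in frequency.

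**3. Pooled placebo.** About 100 patients, 25 per cohort, one in five on placebo, gives about 5 placebo patients per cohort and 20 in all, one quarter of them from each cohort.

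**4. Opportunity, with no drug effect.**

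| | A, B | C | D | Pooled placebo |
|---|---|---|---|---|
| Injections, 52 weeks | 13 | 26 | 52 | (13+13+26+52)/4 = 26 |
| Ratio to pooled | 0.50 | 1.00 | 2.00 | |
| Injections, 6 months | 6 | 13 | 26 | (6+6+13+26)/4 = 12.75 |
| Ratio to pooled | 0.47 | 1.02 | 2.04 | |
| Share of days in FLR window | 2/28 = 7.1% | 2/14 = 14.3% | 2/7 = 28.6% | 14.3% |
| Ratio to pooled | 0.5 | 1.0 | 2.0 | |

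**5. Patient incidence, reactions independent between injections.** The formula is 1 − (1 − p)^n. The risk per injection p is an assumption, since the documents give none; it is the same in every arm. Ratios to pooled placebo over 52 weeks:

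| p | A, B | C | D |
|---|---|---|---|
| 0.1% | 0.51 | 1.00 | 1.98 |
| 1% | 0.56 | 1.04 | 1.85 |
| 2% | 0.61 | 1.07 | 1.71 |
| 5% | 0.74 | 1.12 | 1.41 |
| 10% | 0.87 | 1.09 | 1.16 |

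At 5% over 52 weeks the incidences are 48.7% (A, B), 73.7% (C) and 93.1% (D), against 66.0% pooled. Over 6 months the same 5% gives ratios of 0.60, 1.11 and 1.68.

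**6. Background symptoms that fall in the FLR window by chance (Definition 2).** The formula is 1 − exp(−rate × years × window share). With an assumed 1 listed symptom per patient-year over 0.5 years:
- A, B: 1 − exp(−0.0357) = 3.5%
- C: 1 − exp(−0.0714) = 6.9%
- D: 1 − exp(−0.1429) = 13.3%
- Pooled: 6.8%, so the ratios are 0.52, 1.01 and 1.96.

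Over 0.1 to 2 symptoms per patient-year and 6 to 12 months, D runs from 1.83 to 2.00 and A/B from 0.50 to 0.56.

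**7. Reactions clustered in susceptible patients.** This uses a beta-binomial model with assumed mean risk of 0.5% or 2% per injection and intra-patient correlation of 0.02 to 0.3, over 52 weeks. D is 1.29 to 1.74, C 1.06 to 1.08, and A/B 0.60 to 0.82.

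**8. Masking.** If a 4-weekly regimen doubled the rate in step 6 to 2 per patient-year, its 6-month incidence would be 6.9%. Pooled placebo at the undoubled rate is 6.8%. A true doubling would look like no effect.

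**9. Per-injection percentage.** If p is the same in all arms, its expected value is p in each arm and the ratio to pooled placebo is 1.0.

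**The case against.** The strongest reply is that much of this is already handled.

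- **FLR Definition 2** has the per-injection percentage. A reader might infer that flu-like reactions are compared only per patient; SAP 3.7.2.2 does not support that.
- **LCRIS** events are by definition a subset of ISR Definition 2 events. Their component terms will appear by PT in the ISR per-injection summary (on-study) and in the within-cohort ISR table. A reader might infer that LCRIS has no correction at all; what is missing is only the composite.
- **FLR Definition 1** is nested in Definition 2. Influenza-like illness is already covered per injection by PT. The symptom cluster in its second category is not well described by the isolated-symptom model in step 6.
- **Size and inference.** In groups of about 20, the step 6 example is about 2.7 patients (weekly) or 0.7 (4-weekly) against 1.4 on placebo. No test is specified for these tables; Protocol 10.6 assigns hypothesis testing to efficacy endpoints. Protocol 10.1.4 names treatment-related SAEs and platelet reductions for dose selection, not FLR or LCRIS.
- **Legitimate use.** Per-patient incidence does describe the burden on a patient taking a weekly regimen.

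All of this stands and limits the point to table completeness and reading. It does not remove it. The per-patient tables are still shown beside a placebo column with a different injection frequency. Two composites have no per-injection figure, and FLR has no within-cohort display. The SAP does not say which measure is to be used to compare regimens.

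**Conclusion.** The point holds as a modest bias in the arm-by-arm reading of the per-patient tables for FLR (both definitions) and composite LCRIS. Under no drug effect its direction was the same in every scenario: against the weekly arm and in favour of the 4-weekly arms. The 2-weekly arm is close to neutral (1.00 to 1.14 across the scenarios run).

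The size depends on rates that the documents do not give. It would be tempting to say that the weekly arm will look twice as bad as placebo and the 4-weekly arms half as bad. Those ratios are exact for injection counts over 52 weeks and for FLR-window days. For patient incidence they are rare-event limits, which move towards 1 as the risk per injection rises or as reactions concentrate in fewer patients.

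A comparison of all active arms together with pooled placebo is balanced on frequency by design and is not affected.

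**What to change.** 1. Add the percentage of injections leading to an event for FLR Definition 1 and for composite LCRIS, using the formula already in the SAP.
2. State in SAP 3.7.2.1 and 3.7.2.2 that regimens are compared on the per-injection measures, and that per-patient incidence describes burden within a regimen.
3. Add a within-cohort FLR table and a composite LCRIS row in the planned within-cohort ISR table, labelled as descriptive support only.
4. Footnote the per-patient tables: pooled placebo mixes injection frequencies and volumes (0.50 mL in Cohort B against 0.10 to 0.15 mL elsewhere).

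The cost is a few extra tables and footnotes from data already collected. The within-cohort figures will be very imprecise. With 5 placebo patients and no events, the exact 95% upper limit is 1 − 0.025^(1/5) = 52%. That is why the per-injection measures should lead.
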